## **13. SAFETY ANALYSIS**

### **13.1. Adverse Events (AEs)**

AEs will be coded using MedDRA and will be classified by SOC and PT of MedDRA. All AEs will be captured up through day 56.

Severity: The severity of AEs will be assessed according to the NCI CTCAE v. 4.03 ranging from Grade 1 to Grade 5.

TEAE: A treatment emergent AE (TEAE) is defined as any AE that begins, or any preexisting condition that worsen in severity during the treatment period. For determination of TEAEs during the treatment period, AEs with the greatest severity before baseline will be used as a benchmark for comparison of AEs occurring captured up through day 56.

Relationship (Causality): AEs that have possibly, probably or related relationship to the study drug are defined to be Related to the study drug. Otherwise, the AE will be defined as Not Related. AEs for which the relationship to the study drug is missing will be considered as related to the study drug. AEs with the closest relationship to the study drug will be used for the summary.

TEAEs will be tabulated by subject ID in listings by treatment arm and dose cohort, SOC and PT according to the relationship to study drug(s), the severity and seriousness for the OSP. The following types of TEAEs will be provided:

- Overview of TEAEs
- TEAEs by SOC and PT
- TEAEs by SOC, PT, and Maximum CTCAE toxicity grade
- TEAEs by SOC, PT, and Maximum CTCAE toxicity grade  $\geq 3$
- TEAEs by PT in decreasing frequency
- Drug-related TEAEs by SOC and PT
- Drug-related TEAEs by PT in decreasing frequency
- Serious TEAEs by SOC and PT
- TEAEs leading to death by SOC and PT
- TEAEs leading to treatment discontinuation by SOC and PT

- TEAEs leading to dose interruption by SOC and PT
- TEAEs leading to dose reduction by SOC and PT

If the same PT or SOC is reported more than once for a subject, the subject will only be counted once in the corresponding incidence of PT or the SOC.

To avoid overcounting events for a given PT or SOC, only the most severe and the most closely related PT and/or SOC term will be included for each subject ID in tabulations by severity (i.e., CTCAE toxicity grade) and relationship.

For all subjects in the OSP, AEs, serious AEs and AEs leading to treatment discontinuation will be listed by the subject ID, by the treatment arm and the dose cohort.

In tabulation by severity (i.e., CTCAE toxicity grade) and relationship, for a given PT or SOC, only the most severe and most closely related PT and SOC will be included for each subject.

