7.6. Dose Modification and Dose Delays

Treatment dose delays and dose reductions for individual subjects will be allowed in the event of toxicities, according to the criteria shown in [Table 6](#). If a drug-related Grade 3 or higher AE occurs (excluding nausea and/or vomiting in subjects who did not receive optimal treatment with anti-emetics), the Investigator in conjunction with the Sponsor's Medical Monitor will decide whether the subject will remain on the study. The withheld doses will not be made up; the subject may be allowed to complete dosing according to the remaining schedule.

As mentioned in [Section 7.4](#), fatigue, seizures, headaches, and cerebral or pontine edema are commonly observed in this population and will be recorded according to grade of toxicity, but

will not be considered a DLT unless a relationship to study drug is deemed to be the main contributory factor. If $\geq 33\%$ of subjects experience DLTs, the SRC will convene to determine the course of action. The Medical Monitor or Investigators may request a meeting of the SRC at other times, as deemed clinically indicated.

Table 6: Criteria for Dose Delay and Dose Reduction

Event	Course of Action
Any local injection reaction that requires operative intervention	Hold study drug and contact the Medical Monitor for instructions on resuming dosing
Any local injection reaction that has life-threatening consequences requiring urgent intervention or results in death	Hold study drug and contact the Medical Monitor for instruction on resuming dosing
Any drug-related Grade 3 or higher AE ^a	Hold study drug and contact the Medical Monitor for instruction on resuming dosing

^a Excluding nausea and/or vomiting in subjects who did not receive optimal treatment with anti-emetics

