12.3.3. Treatment Period – Days 0-14

- All assessments should be performed pre-dose, as applicable, unless otherwise stated.
- The site Investigator will communicate with the Medical Monitor during the active dosing period for all subjects on a daily basis regarding clinical status and laboratory values, prior to the patient receiving their daily dose of veledimex, and additionally as clinically indicated.
- Patient contact required daily to discuss clinical status and updates on current/new adverse events. If the patient is discharged prior to Day 14, follow-up may occur via telephone. Successful contact and contact attempts will be documented in EDC.
- Subjects should be instructed to remain in close proximity to the clinical site from Day 0-14.

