12.3.10. Treatment Period Days 8-13

- AEs
- Concomitant medications
- Survival status
- For all subjects, a cohort-specific veledimex dose
- Complete veledimex dose diary
- Patient contact to discuss clinical status and updates on current/new adverse events.
- PI/MM contact regarding clinical status and laboratory values, prior to veledimex administration

12.3.11. Treatment Period Day 14

- Physical examination (including targeted neurological examination)
- Lansky Performance Status, Karnofsky Performance Status, or ECOG status

- Weight
- Vital signs
- AEs
- Concomitant medications
- Survival status
- **Hematology Panel including:** CBC, including WBC count with differential, RBC count, hematocrit, hemoglobin and platelet count, and ESR
- **Coagulation Panel including:** aPTT/PTT and INR
- **Serum Chemistry Panel including:** AST, ALT, LDH, ALP, lipase, amylase, creatinine, total bilirubin, total protein, albumin, BUN, glucose, sodium, potassium, chloride, calcium, phosphorus, CRP, and bicarbonate
- **Urinalysis Panel (dipstick) including:** appearance, pH, specific gravity, glucose, protein/albumin, presence of blood, ketones, bilirubin, nitrates, and leukocyte esterase. In addition, a microscopic exam for casts, crystals, and cells may be done if clinically indicated
- ECG
- For all subjects, a cohort-specific veledimex doseComplete veledimex dose diary
- [REDACTED]
- Blood sample for veledimex PK (Arm 1: [Table 2](#); Arm 2: [Table 3](#))
- [REDACTED]
- [REDACTED]
- MRI scan. CSF may be collected at time of MRI via Ommaya reservoir. Collection is optional.
- Patient contact to discuss clinical status and updates on current/new adverse events.
- PI/MM contact regarding clinical status and laboratory values, prior to veledimex administration
- [REDACTED]

12.3.12. Initial Follow-Up Period Day 15

- AEs
- Concomitant medications
- Survival status
- Blood sample for veledimex PK (Arm 1: [Table 2](#); Arm 2: [Table 3](#))

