### 2.2.3. Projection of Study Duration

The study duration is projected to be approximately 48 months. This assumes that after the enrollment and evaluation of cohort 4 for safety, that the SRC recommends expansion of enrollment into the phase 2 single arm cohort of up to 30 to 35 eligible subjects to obtain at least 30 subjects deemed evaluable for OS. The breakdown of timing suggests:

- Arm 2 enrollment of phase I cohorts is approximately 12 months
- 30 to 35 evaluable DIPG subject enrollment begins one month after the SRC recommends expanding enrollment into a phase 2 component.
- Enrollment to accrue Phase II DIPG subjects is projected to be 12 months.
- Then at least 24 months of follow-up of the last subject enrolled and treated as part of the phase 2 projection.

The overall duration is expected to be up to 2 years and 28 days for an individual subject, assuming:

- Screening period of up 28 days
- Study treatment period of up to 15 days
- Survival status through 24 months from the first dosing date.

In addition, subjects who discontinue or complete study treatment without objective evidence of disease progression should continue to be followed until confirmed disease progression has been documented. Subjects will be followed for survival status for 2 years after enrollment. The active study period refers to the study period from informed consent through the Survival Follow-up Period.

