### 7.1.2. Analysis Visit Window

For safety parameters excluding clinical laboratory data, measurements collected from unscheduled visits will NOT be included in the by-visit summary tables but will be included in the listings. Early termination visits for safety measurements will not be mapped to any scheduled post-baseline visit but will be used as the last assessment during the treatment period.

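### SAP 13.1 ties treatment-emergent AEs to the treatment period instead of Day 56, drops the protocol's drug-related limb and cites CTCAE v4.03, with none of this declared

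*SAP*

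**What the plan says.** SAP 13.1 gives this definition: "A treatment emergent AE (TEAE) is defined as any AE that begins, or any preexisting condition that worsen in severity during the treatment period". Two other sentences in the same section refer to Day 56. One is about capture: "All AEs will be captured up through day 56". The other sets the baseline comparison: "AEs with the greatest severity before baseline will be used as a benchmark for comparison of AEs occurring captured up through day 56". That second sentence opens by again referring to TEAEs in the treatment period.

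The SAP does not define the treatment period. SAP 2.2.3 has "Study treatment period of up to 15 days". Protocol 12.3.3 is headed "Treatment Period – Days 0-14", and protocol 12.3.12 is headed "Initial Follow-Up Period Day 15". Protocol 7.6 adds, on interrupted dosing, "The withheld doses will not be made up". SAP 7.1.2 uses the term differently: an early termination visit "will be used as the last assessment during the treatment period", which concerns safety assessments and not dosing.

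Protocol 16.4.2 has its own TEAE definition. It covers AEs from first dose to the end of the safety evaluation period (Day 56), and baseline events that either worsen or are later judged drug related by the investigator.

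On grading, SAP 13.1 names CTCAE v4.03. Protocol 7.7, 7.8, 14 and 14.4 name v5.0. SAP 13.4 derives laboratory toxicity grades without naming a version.

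Protocol 16 says that the statistical plan will indicate deviations from the protocol's analyses. SAP 6.1, the section on changes, covers the move from summaries to listings and the handling of the Arm 1 data. It does not mention the TEAE definition or the CTCAE version.

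**The concern.** The primary endpoint includes the AE rate, and the TEAE outputs are the planned presentation of AEs by relationship, severity and seriousness. A programmer who codes the defining sentence as it stands would leave out every event starting after dosing ends, although AEs are collected to Day 56. Serious, fatal and drug-related TEAE outputs could all lose events.

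The outputs could also disagree with each other. The DLT window runs to Day 28, so a qualifying Grade 3 DLT starting on Day 20 would be in the DLT summary but missing from the Grade 3 or higher TEAE output.

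The missing drug-related limb and the CTCAE citation are separate departures from the protocol and remain whichever window was meant.

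**Working it through.** The plan gives no figure to reproduce. The check compares texts and counts calendar days, with Day 0 counted as a day. Both arms receive their first study drug on Day 0: veledimex before craniotomy in Arm 1, the vector injection in Arm 2.

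**Window, read literally**

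- Treatment period (protocol 12.3.3): Days 0 to 14 = 15 days.
- TEAE window (protocol 16.4.2): Days 0 to 56 = 57 days.
- Excluded: 57 − 15 = 42 days (Days 15 to 56); 42/57 = 73.7%.
- Day 56 visit held at Day 49: 50 days in all; (50 − 15)/50 = 35/50 = 70.0%.
- Day 56 visit held at Day 63: 64 days in all; (64 − 15)/64 = 49/64 = 76.6%.
- DLT window (SAP 4.3): Days 0 to 28 = 29 days; Days 15 to 28 = 14 days; 14/29 = 48.3%.
- If the period is stretched to include Day 15: 41/57 = 71.9% excluded, and 13 of the 29 DLT days.
- If the period is read as running to Day 56: 0 of 57 excluded.

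Dose delays do not lengthen the literal period, because withheld doses are not made up and dosing ends by Day 14.

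**Outputs.** SAP 13.1 lists 12 types of TEAE output. Three concern dosing actions (treatment discontinuation, interruption, reduction) and should not change. The other 12 − 3 = 9 could lose events with onset on Days 15 to 56.

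**Side by side**

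| Element | Protocol (Amendment 2) | SAP 13.1 |
|---|---|---|
| Window | First dose to end of safety evaluation period, Day 56 | Treatment period; Day 56 appears only in neighbouring sentences |
| Baseline event that worsens | Counted | Counted |
| Baseline event later judged drug related | Counted | Absent |
| CTCAE version | v5.0 | v4.03 |

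The CTCAE comparison is between the SAP and the current protocol. The Amendment 2 summary of changes only shows where v4.03 came from. SAP 1 says the plan serves Amendment 2, and SAP 6.1 excludes table shells for Arm 1 Cohort 1, so that cohort's earlier data do not justify v4.03 for Arm 2.

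**Secondary inconsistency.** Protocol 16.4.2 ends the safety evaluation period early for subjects who leave active follow-up for listed reasons (symptomatic deterioration, loss to follow-up, noncompliance, other) and then follows them for survival only. Protocol 14.2, 14.6 and 14.7 require AEs and SAEs to be recorded through Day 56 without that exception. A recorded event could therefore fall outside the TEAE window.

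**The case against.** The strongest reply is that Day 56 was plainly meant. The sentence after the definition couples the treatment period with Day 56, and SAP 7.2.4 tests treatment emergence against first dose with no Day 14 cutoff. The Day 14 limit comes from protocol visit headings and a study-duration bullet, not from a TEAE rule. On that reading the window is an undefined term and not a deviation, so it needs no declaration. This stands as to intent. It does not rescue the text: the SAP's own duration figure is up to 15 days, its schedule separates treatment from initial follow-up, and the paragraph has to be overridden by inference to give the protocol's answer.

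Other points limit the effect:

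- The percentages are calendar days, not events. This stands.
- The omitted limb is narrow. Under protocol 14.5, an event starting before study drug is reported as an AE only if protocol related, and SAP 13.1 already counts worsening. This stands, but the limb is still a difference from the protocol.
- Investigators grade AEs under protocol 14.4, and the documents do not show that the two CTCAE versions grade any item differently. This also stands. The version does not decide whether a new-onset AE is counted. It matters for the laboratory grades in SAP 13.4, where no version is named, and for any pooling with Arm 1 Cohort 1.
- The Grade 3 or higher TEAE output uses the OSP and the DLT summary the ESP, so they need not match. This carries little weight: SAP 5.3 makes the ESP a subset, so a Grade 3 DLT in the ESP should also appear in the OSP output.
- SAP 6.1 describes the major change and may not be exhaustive. Even so, protocol 16 calls for deviations to be indicated in the plan, and the missing limb is not indicated.

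**Conclusion.** The concern holds, as a minor one. The defining sentence conflicts with protocol 16.4.2 and with the Day 56 comparison beside it. The drug-related limb is missing, the CTCAE version is superseded, and SAP 6.1 is silent on all of this.

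The figures of 42 of 57 days and 9 of 12 outputs apply only if the sentence is programmed literally with the protocol's Days 0 to 14. On the Day 56 reading no days are lost. The effect on AE rates is unknown. The OSP listings of all AEs, the DLT summary with its own Day 0 to 28 window, and escalation decisions are unaffected.

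**What to change.** In SAP 13.1:

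- Define a TEAE as onset or worsening from the first dose of either study drug through the protocol 16.4.2 safety evaluation period (Day 56).
- Add baseline events later considered drug related by the investigator.
- Remove the treatment-period wording from both sentences where it occurs.
- Cite CTCAE v5.0 here and in SAP 13.4, and state the version used for Arm 1 Cohort 1 if its data are pooled.

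If any difference from protocol 16.4.2 is deliberate, declare it in SAP 6.1.

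As a secondary step, reconcile the early end of the safety period in protocol 16.4.2 with Sections 14.2, 14.6 and 14.7, so that AEs recorded through Day 56 are counted.

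The cost is a few SAP sentences and, for the secondary step, one protocol paragraph. No new visits or data are needed. Compared with the literal reading, TEAE counts may rise and may include more disease-related events.

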16.4.2. Safety Analyses

For the first veledimex dose cohorts in Arms 1 and 2 (*i.e.*, Cohorts 1 and 3, respectively), a minimum of three ESP subjects must be eligible for evaluation of safety. In addition, evaluation of any DLTs will be performed according to protocol-defined criteria. Safety variables will be tabulated and presented by arm and by dose cohort.

Safety evaluations will be based on the incidence, intensity, and type of AEs and SAEs. Clinically significant changes in the subjects' physical examinations, vital signs, ECG evaluations, and abnormal laboratory values will be captured as AEs. Safety will also be assessed based on medical history and prior/concomitant medications.

The safety evaluation period extends from the date the subject signs the ICF or assent form, as applicable, through the Initial Follow-up Period (Day 56), unless the subject discontinues from active follow-up due to one of the following reasons:

- Symptomatic deterioration also denoted symptomatic progression
- Loss to follow up
- Noncompliance with the protocol
- Other reason not listed above

Exposure to study drug(s) and reasons for discontinuation of study treatment will be tabulated. All treatment emergent- AEs (TEAEs) will be coded according to the System Organ Class and Preferred Term using the Medical Dictionary for Regulatory Activities (MedDRA). The TEAEs will be tabulated by number and percent of subjects according to relationship to the study drug(s), severity, and seriousness. A TEAE is defined as any AE that occurs during or after administration of the first dose of study drug through the evaluation period for safety defined above, regardless of relationship to study drug; or any event that is present at baseline that worsens in intensity or is subsequently considered to be drug related by the Investigator. Deaths, SAEs, and AEs resulting in study discontinuation will be listed.

After the conclusion of the safety evaluation period is triggered by a discontinuation event, the subject continues to be followed only for OS.

Laboratory parameters will be summarized by visit. Listings of vital signs and physical examination data will be listed by visit.

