#### **4. STUDY ENDPOINTS AND EVALUATIONS FOR PHASE I COHORTS**

#### 4.1. Study Endpoints

#### 4.1.1. Primary Endpoint

- Assessment of safety and tolerability of Ad-RTS-hIL-12, administered by intratumoral injection plus veledimex administered PO, as determined by the AE rate and the occurrence of DLTs analyzed specifically for each cohort.

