### 7.1.1. Baseline Definition

The day of Ad-RTS-hIL-12 administration is designated as Day 0. Baseline value for safety and demographic data is defined as the last non-missing value closest, but prior to, the first dose of study drug veledimex or Ad-RTS-hIL-12. For tumor assessment, a baseline MRI will be performed within 72 hours of Ad-RTS-hIL-12 administration (Day 2).

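### SAP 13.1 judges treatment emergence against the worst pre-baseline severity, contrary to protocol 16.4.2 and SAP 7.1.1, and so can undercount TEAEs

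*SAP*

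**What the plan says.** SAP 13.1 first defines a TEAE in two limbs: "any AE that begins, or any preexisting condition that worsen in severity during the treatment period". It then sets the yardstick: "AEs with the greatest severity before baseline will be used as a benchmark for comparison of AEs occurring captured up through day 56". No look-back limit is given, and there is no limb for events later attributed to study drug.

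Protocol 16.4.2 has a different rule. Its first limb reads "A TEAE is defined as any AE that occurs during or after administration of the first dose of study drug" and runs to the end of the safety evaluation period, whatever the relationship to drug. Its second limb adds "any event that is present at baseline that worsens in intensity or is subsequently considered to be drug related by the Investigator".

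SAP 7.1.1 fixes the reference point for safety data in general: "Baseline value for safety and demographic data is defined as the last non-missing value closest, but prior to, the first dose of study drug", whether that drug is veledimex or the vector. That is the latest pre-dose value, not the worst.

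The primary endpoint in SAP 4.1.1 and protocol 16.3.1 is safety and tolerability, "as determined by the AE rate and the occurrence of DLTs analyzed specifically for each cohort". Protocol Section 16 says that departures from its analyses will be indicated in the statistical plan. SAP 6.1, which lists the changes, does not mention the TEAE definition.

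**The concern.** A worst-ever benchmark and an at-baseline benchmark give different answers when a symptom eases before dosing and returns afterwards. The entry criteria make such a course plausible. Subjects must have recovered from the toxic effects of earlier treatment and must have been on a steady or falling dexamethasone dose for a week. Arm 2 subjects enter 2 to 10 weeks after radiotherapy.

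The DLT definition is a partial safeguard for neurological events. In Arm 2, transient neurological changes become DLTs only if they last more than 10 days. Seizures, headaches and cerebral or pontine edema count only if study drug is the main contributor. For these events the TEAE outputs are where a signal would be expected to show. Every AE output by organ class, preferred term, grade or relationship in SAP 13.1 is a TEAE output, so these would in practice supply the AE-rate component of the primary endpoint. If the SAP rule and the protocol rule were both followed, two programmers could produce different safety tables from the same database.

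**Working it through.** The plan states no figure on this point, so there is none to reproduce. The check compares the two rules case by case.

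**Notation.** M is the worst CTCAE grade before baseline (1 to 4). B is the grade at first dose (0 means resolved). P is the grade after injection. The SAP 13.1 benchmark requires P > M. Protocol 16.4.2 requires P > B, a new event, or a baseline event later judged drug related.

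**Direction.** M cannot be below B, so P > M implies P > B. The SAP benchmark can therefore remove TEAEs relative to the protocol but cannot add any.

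**Worked cases.**

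| M | B | P | Protocol 16.4.2 | SAP 13.1 benchmark |
|---|---|---|---|---|
| 3 | 1 | 3 | TEAE | not a TEAE |
| 3 | 1 | 4 | TEAE | TEAE |
| 3 | 0 | 2 | TEAE | fails the benchmark, but could count as an AE that begins |
| 3 | 3 | 3 | TEAE only if later judged drug related | not a TEAE |

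**Count of possible courses.** Take all courses that improved before dosing (B from 0 to M − 1) and worsened after it (P from B + 1 to 5).

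- For each M the number of courses is the sum of (5 − B) over B: 5, 9, 12 and 14 for M = 1, 2, 3 and 4. The total is 40, and the protocol counts all 40.
- Courses failing the SAP benchmark have P ≤ M. For each M their number is M(M + 1)/2: 1, 3, 6 and 10. The total is 20 of 40.
- Of these 20, the symptom had resolved (B = 0) in 1 + 2 + 3 + 4 = 10. Here the SAP's two sentences conflict. In the other 10 the symptom was still present at first dose, and exclusion follows from the benchmark sentence.

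These are counts of possible courses, not expected frequencies.

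**Effect of one subject on a cohort TEAE proportion.** It is 100/n percentage points. The protocol synopsis plans 3 to 6 subjects per cohort and an expansion of up to 30. This gives 33.3 points at n=3, 16.7 at n=6 and 3.3 at n=30.

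**Chance that a cohort is touched.** The documents give no rate for such courses, so the share q of subjects affected is an assumption. The chance of at least one is 1 − (1 − q)^n.

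| q (assumed) | n=3 | n=6 |
|---|---|---|
| 10% | 27% | 47% |
| 20% | 49% | 74% |
| 30% | 66% | 88% |

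**The case against.** A reader might infer that the affected events vanish from the primary safety endpoint. The documents do not support that. The endpoint is worded as AEs plus DLTs, not as TEAEs. The DLT criteria in protocol 7.4 and SAP 4.3 carry no treatment-emergence condition. Escalation and the recommended dose rest on DLTs in the Evaluable Safety Population. The Grade 3 to 1 to 3 example can still be a DLT if it meets the relatedness and duration criteria. SAP 13.1 also lists all AEs and SAEs by subject whatever their TEAE status, and SAP 6.1 prefers listings to summaries for very small samples. All of this stands. What remains exposed is TEAE classification and the outputs built on it.

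A reader might also infer that every event at or below its pre-baseline peak is lost. That is too broad. An event whose grade has not changed since baseline is not a worsening under the protocol either. Recurrence after full resolution can be read as an AE that begins on treatment. SAP 7.2.4 imputes partial onset dates in order to decide treatment emergence, so onset date matters. If a site enters a worsening as a new AE with an on-study onset, the first limb might even rescue a symptom that had not resolved. This shows that the SAP can be read two ways; it does not remove the literal effect of the benchmark sentence.

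The reach of the benchmark is also uncertain. Under protocol 14.5, pre-dose events unrelated to a study procedure go to Medical History rather than the AE form. Protocol 14.2 asks for a grade for ongoing symptoms recorded there. The SAP does not say whether those grades feed the benchmark. If they do not, many disease and radiotherapy symptoms would escape it. That limits the likely size and is itself a gap.

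Finally, a reader might attach a definite share of subjects to the problem. No passage supports one.

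**Conclusion.** The conflict is established from the text: SAP 13.1 departs from protocol 16.4.2 on the comparison point and on the drug-related limb, departs from SAP 7.1.1 on what baseline means, and is not declared in SAP 6.1. Followed literally, it undercounts in one direction only. Exclusion is clear for a symptom that had improved, was still present at first dose, and re-worsened to no more than its earlier peak. It is ambiguous for a resolved symptom that recurs. Re-worsening above the earlier peak still counts.

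The dropped limb has a further consequence. A baseline event that the investigator later attributes to study drug can be missing from the drug-related TEAE outputs.

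The consequence is confined to the TEAE outputs. How often it would occur cannot be derived from the documents; the 10% to 30% range is illustrative only. In cohorts of 3 to 6, however, a single reclassified subject visibly changes the reported proportion, or the TEAE listing where no proportion is shown.

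**What to change.** Before the Arm 2 database is locked, amend SAP 13.1 in four respects:

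- Replace the benchmark with the severity at the last assessment before the first dose of any study drug. Naming any study drug matters because Arm 1 takes veledimex on Day 0 before resection, whereas Arm 2 starts with the injection.
- State that a condition resolved before first dose that recurs at or after first dose is a new TEAE, at any grade.
- Restore the protocol's second limb in full: "any event that is present at baseline that worsens in intensity or is subsequently considered to be drug related by the Investigator".
- State that Medical History grades of symptoms ongoing at first dose serve as the baseline grade.

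If the sponsor prefers the worst-before-baseline rule, it should instead be declared and justified in SAP 6.1, with a look-back period and the data source named.

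The cost is a few sentences and a change to the TEAE derivation. No new data are needed, since protocol 14.2 already asks for the grades of ongoing symptoms. The downside is that the TEAE count may rise slightly.
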